## 20.4 Sample Size

We will phone screen approximately 600 participants, and enroll approximately 150 participants to randomize a total of 48 participants (through week 6/T8). In this pilot study sample sizes are obviously quite limited. A simple t test of mean differences requires an effect size of .939 to have .8 power. We have chosen an unbalanced design with more subjects on CBD to maximize the ability to characterize response to treatment for use in planning future confirmatory trials and still have valid hypotheses tests.

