Participants in [name] clinical trial "Leveraging Biomarkers for Personalized Treatment of AUD Comorbid with PTSD" (IRB # s18-01405) who are determined to be ineligible will be evaluated for eligibility in this trial. Consenting participants' data will be linked to this study and procedures completed under the Biomarkers trial will not be duplicated for this trial except at PI or co-Investigator discretion.

Based on successful recruitment in current and past AUD and PTSD trials at NYULMC, we do not expect any significant barriers to recruitment. If recruitment lags, strategies would include altering staffing patterns and increasing advertisement and outreach to clinical programs. To maximize rates of completion of the follow-up visit, we will follow procedures that have been successful in retaining patients with similar demographics, e.g. drug using emergency department patients, for whom we have achieved follow-up rates of 85% at 6 months. If follow-up rates at 10 weeks are below 90%, we will reexamine our tracking procedures, and consider altering the reimbursement and/or completing community-based follow-ups.

We expect the population to be approximately 50% male, 50% female; 7% Hispanic, 60% Non-Hispanic Caucasian, 30% Non-Hispanic African American, and 3% other.

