## 5.6 Total Number of Participants and Sites

Recruitment will end when approximately 150 participants are enrolled. It is expected that approximately 48 participants who fully meet study criteria will be randomized in a 5:3 ratio to receive either 600mg CBD/day (PO) or placebo respectively (N=30 participants on CBD and N=18 participants on placebo).

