### 20.3 Description of Statistical Methods

### 20.3.1 General Approach

We recognize that the relatively small sample sizes proposed in the RCT are not likely to produce statistical significance, unless the effect sizes are remarkably high. We will carry out a full Mixed Model Repeated Measures (MMRM) statistical analysis in case CBD does perform so well. However, the main focus of the statistical analysis of the results of the trial will be to characterize the effect sizes and response rates across the various measurement domains and the profiles of individuals who are treatment successes. The intent to treat (ITT) population will contain all randomized patients who receive at least one dose of double-blind study medication and from whom at least one post-baseline (B1) efficacy measurement is obtained while on study medication. The efficacy analysis will be based on the ITT population. Two-sided hypothesis testing will be utilized. Tests with p-values less than or equal to 0.05 will be considered statistically significant, while those less than equal to 0.10 will be considered suggestive. Since this trial is the first use of this treatment for this diagnostic indication, no adjustments of p-values for multiple comparisons will be made. Thus, all control of type 1 error is contrast-wise. All confidence intervals will be two-sided with 95% confidence. Mean treatment effect, standard errors, and 95% confidence intervals will be derived from fully adjusted models on outcomes averaged across the treatment period. Cohen's d and p-values will be calculated from fully adjusted models with appropriately transformed outcome variables. For dichotomous drinking outcomes, prevalence rates will be calculated. Odds ratios (ORs) and p-values will be derived from logistic regression models including treatment group.

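### The only power figure (d = .939 for 80% power) does not fit the stated 30:18 randomisation; it matches 40 participants split 25:15, a number the plan never mentions

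*Combined protocol and SAP*

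**What the plan says.** Section 20.4 is the only place where the plan quantifies power. It intends to "enroll approximately 150 participants to randomize a total of 48 participants (through week 6/T8"), and then states: "A simple t test of mean differences requires an effect size of .939 to have .8 power". The sentence gives no arm sizes, significance level or dropout allowance. The section goes on to explain the unequal allocation: "We have chosen an unbalanced design with more subjects on CBD to maximize the ability to characterize response to treatment".

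The missing inputs have to be taken from elsewhere:

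- **Arm sizes.** Section 5.6 gives "N=30 participants on CBD and N=18 participants on placebo". The protocol summary and sections 2.3, 4.1 and 20.5.1 give the same split.
- **Test.** Section 20.3.1: "Two-sided hypothesis testing will be utilized", and "Tests with p-values less than or equal to 0.05 will be considered statistically significant".
- **Multiplicity.** Section 20.3.1: "no adjustments of p-values for multiple comparisons will be made". Section 20.3.8 also declines any correction.
- **Attrition.** No planning rate is given. Section 5.7.2 says that dropouts are not replaced. Section 5.4 gives an operational threshold: "If follow-up rates at 10 weeks are below 90%, we will reexamine our tracking procedures".

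**The concern.** A detectable effect size for a two-sample t test is fixed by the two arm sizes, the significance level and the power. The plan states all four, but the effect size it reports does not follow from them. The reader is left with two readings. Either the calculation assumes no dropout and used the wrong sample size, or it assumes about 40 evaluable participants and does not say so. The second reading implies a loss of about 17%, which the plan does not reconcile with the week 6 wording attached to the 48 or with the 90% follow-up threshold.

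The trial's stated purpose is to characterise effect sizes for planning confirmatory trials, so what the sample can and cannot show should be stated correctly. Section 20.1 says that a formal SAP is still to be written before database lock, and an uncorrected figure could be carried into it and into the report.

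**Working it through.** **Inputs.** n1 = 30 and n2 = 18 (section 5.6); two-sided alpha = 0.05 with no split (section 20.3.1); power = 0.80 and d = .939 (section 20.4).

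**Formula.** For a two-sample t test with standardised difference d, the degrees of freedom are n1 + n2 − 2 and the noncentrality is d × √(n1·n2/(n1 + n2)). Power is the probability that a noncentral t variable with these parameters falls outside ± the two-sided critical value. The detectable d is found by setting power to 0.80 and solving.

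**Step 1: reproduce the plan's figure at its stated size.** With 30 and 18, df = 46 and √(30 × 18/48) = √11.25 = 3.354.

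- Solving for 80% power gives d = 0.853, not .939. The normal approximation gives 0.835, so the choice of formula does not explain the gap.
- At d = .939 the noncentrality is .939 × 3.354 = 3.149 and the power is 86.9%, not 80%.

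**Step 2: look for a setting that gives .939.**

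| Setting | Detectable d at 80% power | Power at d = .939 |
|---|---|---|
| 30:18, two-sided 0.05 (as stated) | 0.853 | 86.9% |
| 24:24, two-sided 0.05 | 0.826 | 89.0% |
| 30:18, one-sided 0.05 | 0.753 | 92.8% |
| 30:18, two-sided 0.025 | 0.945 | 79.4% |
| 27:16 (about 90% of 48), two-sided 0.05 | 0.905 | 82.8% |
| 26:15, two-sided 0.05 | 0.932 | 80.6% |
| 25:15, two-sided 0.05 | 0.939 | 80.0% |

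Raising the power at 30:18 does not produce .939 either: 85% power gives 0.913 and 90% power gives 0.987. Halving alpha for two endpoints comes close at 0.945, but it misses the stated value and section 20.3.1 excludes it.

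A search over all pairs of arm sizes from 10 to 40 (two-sided 0.05, 80% power) found two within 0.0006 of .939: 25:15 (0.9389) and 21:17 (0.9393). Only 25:15 has the trial's 5:3 ratio.

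**Step 3: size of the discrepancy.**

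- In d: .939 − .853 = .086, and .086/.853 = 10%.
- In power: 86.9% − 80% = 6.9 percentage points.
- Loss needed to go from 48 to 40: 8/48 = 16.7%, that is 83.3% retained. The 90% threshold of section 5.4 would leave 0.90 × 48 = 43.2, or about 27:16.

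**Step 4: precision.** Near d = 0, the half-width of the 95% confidence interval for d is about t × √(1/n1 + 1/n2). For 30:18 this is 2.013 × 0.298 = 0.60. For 25:15 it is 2.024 × 0.327 = 0.66.

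**The case against.** The strongest reply is that .939 may be a correct figure for an unstated evaluable sample. Section 6.1.9 admits to the primary analyses only those who complete the six weeks, and section 5.7.2 expects some losses without replacement. On that footing, power based on fewer than 48 is appropriate, and 25:15 keeps the 5:3 ratio exactly. Section 5.4 reports 85% follow-up at 6 months in a comparable population, close to the 83% that 40 of 48 implies. The 90% in the same section triggers a review of tracking procedures and is not a planning assumption. On this view the figure is under-documented rather than wrong.

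This reading is possible, and it limits what can be claimed: the plan does not flatly contradict an allowance for loss. But the plan does not state one. Section 20.4 names only 48, and section 20.3.1 bases the efficacy analysis on an intention-to-treat set that needs just one post-baseline measurement. That definition conflicts with section 6.1.9 and leaves the evaluable number open.

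It is also fair to say that the discrepancy is conservative, that both 0.85 and 0.94 are large effects, that section 20.3.1 already concedes that significance is unlikely, and that 48 is not derived from .939. These points limit the consequence. They do not make the sentence correct for the design it describes.

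**Conclusion.** The concern holds. For 30 and 18 participants with complete data, a two-sided 0.05 t test has 80% power for d = 0.853. The stated .939 is about 10% too large, and power at that value is 86.9%. This rests on the plan's own arm sizes and testing rules and on the simple t test it names; the MMRM with baseline covariate that will actually be used is a different calculation.

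That .939 was computed for 25:15 is an inference from a match to three decimals at the trial's exact ratio. It could be left over from another sample size or reflect an undisclosed loss of 16.7%; the plan does not show which. The practical effect is modest: the error understates power, and no sample size, endpoint or decision rule depends on it. It should still be corrected, because it is the only power figure in the plan and the stated design does not produce it.

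**What to change.** Replace the sentence in section 20.4 with, for example: *With 30 and 18 participants, a two-sided 0.05 t test has 80% power for d = 0.85. If only about 40 (25 and 15) provide week 6 data, it has 80% power for d = 0.94.* State which of the two is the planning case and, if it is the second, give the retention it assumes (about 83%).

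As an optional addition, give the expected 95% confidence interval half-width for d (about 0.60 at 30:18 and 0.66 at 25:15), since estimating effect sizes is the stated focus.

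The cost is a sentence or two in section 20.4, carried into the formal SAP. The number of participants and the analysis do not change.

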### 20.5 Measures to Minimize Bias

### 20.5.1 Enrollment/Randomization/Masking Procedures

Enrolled participants that pass screening will be randomized using a 5:3 ratio to receive either 600mg CBD/day (PO) or placebo respectively for 6 weeks (N=30 participants on CBD and N=18 participants on placebo). Treatment assignment will be known only to a designated unblinded study staff member in charge of dispensing study medication under direct PI supervision, but the blind can be broken if necessary, e.g., in case of a serious reaction during drug administration.

#### 20.5.2 Evaluation of Success of Blinding

In order to assess the integrity of the blind, following the treatment portion of the study (T8), participants will be asked to guess 1) what medication was administered (CBD or placebo), and 2) degree of confidence in this guess.

#### 20.5.3 Breaking the Study Blind/Participant Code

The blind can be broken for an individual participant if necessary, e.g., in case of a serious reaction during drug administration or in the event of a SAE likely to be related to the study medication.

## 21 Source Documents and Access to Source Data/Documents

Source data is all information, original records of clinical findings, observations, or other activities in a clinical trial necessary for the reconstruction and evaluation of the trial. Source data are contained in source documents. Examples of these original documents, and data records include: hospital records, clinical and office charts, laboratory notes, memoranda, subjects' diaries or evaluation checklists, study medication dispensing records, recorded data from automated instruments, copies or transcriptions certified after verification as being accurate and complete, microfiches, photographic negatives, microfilm or magnetic media, x-rays, subject files, and records kept at the dispensation site, at the laboratories, and at medico- technical departments involved in the clinical trial. It is acceptable to use CRFs as source documents. If this is the case, it should be stated in this section what data will be collected on CRFs and what data will be collected from other sources.

The study case report form (CRF) is the primary data collection instrument for the study. All data requested on the CRF must be recorded. All missing data must be explained. If a space on the CRF is left blank because the procedure was not done or the question was not asked, write "N/D". If the item is not applicable to the individual case, write "N/A". All entries should be printed legibly in black ink. If any entry error has been made, to correct such an error, draw a single straight line through the incorrect entry and enterthe correct data above it. All such changes must be initialed and dated. DO NOT ERASE OR WHITE OUT ERRORS. For clarification of illegible or uncertain entries, print the clarification above the item, then initial and date it.

Access to study records will be limited to IRB-approved members of the study team. The investigator will permit study-related monitoring, audits, and inspections by the IRB/EC, the sponsor, government regulatory bodies, and University compliance and quality assurance groups of all study related documents (e.g. source documents, regulatory documents, data collection instruments, study data etc.). The investigator will ensure the capability for inspections of applicable study-related facilities (e.g. dispensation site, diagnostic laboratory, etc.).

Participation as an investigator in this study implies acceptance of potential inspection by government regulatory authorities and applicable University compliance and quality assurance offices.

# 22 Quality Assurance and Quality Control

Data quality assurance (QA) includes all those planned and systematic actions that are established to ensure that the trial is performed and the data are generated, documented (recorded), and reported in compliance with GCP and the applicable regulatory requirements(s) (ICH E6 1.46). Data quality control (QC) includes the operational techniques and activities undertaken within the quality assurance system to verify that the requirements for quality of the trial-related activities have been fulfilled (ICH E6 1.47).

QC procedures will be implemented beginning with the data entry system, and data QC checks on the database will be generated. Any missing data or data anomalies will be communicated to the site(s) for clarification/resolution.

Following written SOPs, the monitors will verify that the clinical trial is conducted and data are generated,

documented (recorded), and reported in compliance with the protocol, GCP, and the applicable regulatory requirements (e.g., Good Laboratory Practices (GLP), Good Manufacturing Practices (GMP)). The investigational site will provide direct access to all trial related sites, source data/documents, and reports for the purpose of monitoring and auditing by the sponsor, and inspection by local and regulatory authorities.

# 23 Ethics/Protection of Human Subjects

## 23.1 Ethical Standard

The investigator will ensure that this study is conducted in full conformity with Regulations for the Protection of Human Subjects of Research codified in 45 CFR Part 46, 21 CFR Part 50, 21 CFR Part 56, and/or the ICH E6.

## 23.2 Institutional Review Board

The protocol, informed consent form(s), recruitment materials, and all participant-facing materials will be submitted to the IRB for review and approval. Study approval must be obtained before any participant is enrolled. Any amendment to the protocol will require review and approval by the IRB before the changes are implemented to the study. All changes to the consent form will be IRB approved; a determination will be made by the IRB regarding whether previously consented participants need to be re-consented.

## 23.3 Informed Consent Process

## 23.3.1 Consent/Assent and Other Informational Documents Provided to Participants

Consent forms describing in detail the study agent, study procedures, and risks are given to the participant and written documentation of informed consent is required prior to starting intervention/administering study product.

### 23.3.2 Consent Procedures and Documentation

An IRB-approved pre-screening form will be used to pre-screen individuals expressing interest in the study, to assess whether they are likely to qualify for the study. Interested patients who pass the pre-screening (conducted via phone) will be referred for a screening visit.

• Participants will be provided with an informed consent form, COVID-19 information sheet, audio and video consent form, and health release form at or prior to their screening visit. Understanding of the study procedures will be assessed using a consent quiz.

Subjects will be electronically consented via a 21CFR Part 11-compliant electronic consent method. The U.S. Food and Drug Administration (FDA)'s MyStudies mobile application is a Part 11-compliant electronic consent method which allows our study team to review study informed consent forms with the participants remotely and obtain the participant's electronic signatures on the study's informed consent forms via the mobile application. The app is available in the US in English on both Apple and Android smartphones. Secure registration allows participants to enter a unique enrollment code specific to our study to prevent people outside of the study from enrolling. The application allows for the storage of signed electronic consent forms on HIPAA and FISMA compliant servers; the participant is able to receive secure copies of their electronically signed consent form PDF by email directly after they sign the consent. Designated research staff can easily access and download all signed consent forms for secure storage on the shared drive by logging into a portal. The FDA MyStudies e-consent application will not be used until a link to the informed consent form has been submitted and approved by NYU's IRB. We will also utilize REDCap (accompanied with REDCap Cloud, a Part 11-compliant electronic consent forms remotely.

Alternatively, remote consent may be obtained via SendSafe email. In this case, a copy of the consent form will be sent via SendSafe email. The subject's signature will be captured electronically on the document provided, or the subject may print and sign a physical copy that is scanned and returned via the SendSafe method. Subjects who do not have access to email or scanner may choose to have a hard copy of the consent mailed to them and return via a self-addressed stamped envelope provided by the study team.

At or prior to their first visit, participants will be provided with an informed consent form including all pertinent details of the study including descriptions of the following: the assessment interview and questionnaires; the follow-up interviews; description of experimental treatment; risks and benefits of study procedures; alternatives

#### #S17-00949

to participation in the study; confidentiality; emergency treatment and compensation for injury; payment for participation; a statement that patients will be informed of any new findings affecting the risks or benefits of the study; a statement that participation is voluntary and that the patient may withdraw at any time; and information about whom to contact with questions or in case of emergency. The consent form will also include assurances of confidentiality and a statement that participation is entirely voluntary, that the decision to participate will in no way influence other aspects of the patient's treatment, and that the participant is free to withdraw participation at any time. Study staff will explain the research study to the participant and answer any questions that may arise. All participants will receive a verbal explanation in terms suited to their comprehension of the purposes, procedures, and potential risks of the study and of their rights as research participants. Participants will have the opportunity to carefully review the written consent form and ask questions of the study team.

Participants must pass a consent quiz with a score of 90% or higher prior to signing. Participants who score less than 90% may take the quiz a second time after the study team has reviewed content and answered all questions. Participants who are unable to score 90% or higher on the quiz after two attempts will be given a copy of the consent to take home and may return for a screening visit on a later date. If the participant is unable to score 90% or higher on the study unless otherwise determined by senior management or the PI. If a decision is made to retain the subject despite failure to attain a 90% or higher on the consent quiz, the rationale will be documented in the subject's binder via a note to file.

A copy of the signed informed consent document will be given to the participants for their records. The rights and welfare of the participants will be protected by emphasizing to them that the quality of their medical care will not be adversely affected if they decline to participate in this study. The participants may withdraw consent at any time throughout the course of the trial.

A copy of the signed informed consent document will be stored in the subject's research record. The consent process, including the name of the individual obtaining consent, will be thoroughly documented in the subject's research record. Any alteration to the standard consent process (e.g. use of a translator, consent from a legally authorized representative, consent document presented orally, etc.) and the justification for such alteration will likewise be documented.

Patients who consent to participate in the study will also be invited to consent to having their remote and/or inperson screening assessments (i.e. SCID and CAPS) audio-recorded at the initial visit (see Audio Recording Consent) for quality control and for voice-markers analysis. If a patient does not sign the Audio Recording Consent, then we will not audio-record the patient's interview.

